### 5.3 Study Population

Participants who have been diagnosed with insomnia between the ages of 22-64 years will be enrolled in this study.

We will recruit 50 participants from YNHH, which represents a geographic and racial diversity of populations as well as diversity of patients attending sleep clinics in the US. YNHH is the largest and most comprehensive healthcare system in Connecticut (1,541-bed tertiary care hospital with 12,000 employees). Last year YNHH treated over 70,000 inpatients and more than 800,000 outpatient visits. The medical staff exceeds 3,500, and it serves as the primary teaching hospital for the Yale School of Medicine. Women and minorities are strongly represented in the population. More specifically, the gender racial mix is approximately 51% women; 50% White, not of Hispanic Origin; 33% Black, not of Hispanic Origin, 15% Hispanic; 1% Asian and 1% other. Approximately 42% of patients have private insurance, 29% have Medicare, 27% are covered by Medicaid or other public assistance, and 2% are uninsured.

Patients from YNHH will be recruited from the Yale Sleep Center. This center opened in 1997 and became accredited by the American Academy of Sleep Medicine (AASM) the same year. The Yale Sleep Center is renowned nationally and internationally for its excellence in clinical care and research. It is a multidisciplinary center with active participation of faculty from various departments in clinical, research and educational missions of the Center. The Yale Sleep Center has performed over 11,078 polysomnographies and numerous Multiple Sleep Latency Tests (MSLT). The Yale Sleep Center has become a major referral center in Connecticut, performing about 200 polysomnographies and 4 MSLTs each month. The Center is comprised of three fully American Academy of Sleep Medicine (AASM) accredited centers with a total of 15 monitored bed units. The Center receives referrals from all Connecticut counties as well as northeast states. The YNHH Sleep Medicine program offers comprehensive diagnostic testing and treatment services for those who are unable to get a restful night sleep. As an interdisciplinary program, clinicians work closely with a network of specialty providers who are board-certified in bariatric surgery, cardiology, dentistry, neurology, otolaryngology and psychology. The program is accredited by the AASM.

Patients from Mayo Clinic will be recruited from the Mayo Center for Sleep Medicine. This center opened in 1983 and became accredited by the AASM in 1985. The Mayo Center for Sleep Medicine is renowned nationally and internationally for its excellence in clinical care and research. It is a multidisciplinary center with active participation of faculty from various departments in clinical, research and educational missions of the Center. The Mayo Center for Sleep Medicine has performed over 120,000 polysomnograms (PSG), Multiple Sleep Latency Tests (MSLT), Maintenance of Wakefulness tests (MWT), and Home Sleep Apnea Tests (HSAT). The Mayo Center for Sleep Medicine has become a major national and international referral center performing about 330 PSGs, 100 HSATs and 15 MSLTs and MWTs each month. The Center is accredited by the American Academy of Sleep Medicine (AASM) and operates 24 monitored

beds. The Center receives referrals primarily from Minnesota, Wisconsin, Iowa, Illinois, and North and South Dakota with a significant volume of national and international referrals.

### 5.3.1 Number of Participants

We will enroll 50 patients at YNHH and 50 patients at the Mayo Clinic (100 total). Approximately 350 patients are anticipated to be screened at Yale.

### 5.3.2 Eligibility Criteria/Vulnerable Populations

Inclusion Criteria:

- Age between 22-64 years
- English-speaking (both reading and writing in English required)
- Diagnosis of chronic insomnia
- Participant is willing and able to give consent and participate in study
- Participant has an email account or is willing to create one and a smartphone able to download the necessary applications
- Participant is willing and able to use the PDT, the Hugo data sharing platform and the syncable devices (e.g. Fitbit)
- Participant has primary care at YNHH or Mayo Clinic

Exclusion Criteria:

- Pregnancy
- Shift work or family/other commitments that interfere with establishment of regular night-time sleep patterns, and if wake/sleep time is outside the ranges of 4:00h – 10:00h (wake time) and 20:00h – 02:00h (bed time)
- Absence of a reliable internet access and smartphone
- A reported diagnosis of psychosis, schizophrenia or bipolar disorder, or any medical disorders contraindicated with sleep restriction
- Current involvement in a **non-medication** treatment program for insomnia (participants are still eligible if they are taking traditional sleep medications)
- Those with untreated co-existing sleep conditions (e.g. sleep apnea)
- Those who have failed CBT for insomnia in the past

## 6 Methods

### 6.1 Treatment – Device

#### 6.1.1 Intended Use for Device (provide the following information for each device being investigated in the study)

The PDT being studied in this protocol was authorized by the FDA under the name Somryst. The PDT has not been modified from its usual commercial state for this study. Somryst is intended to improve insomnia symptoms by providing neurobehavioral intervention (cognitive behavioral therapy for insomnia – CBT-I) to adults 22 years of age and older with chronic insomnia. This study will evaluate outcomes in adults age 22-64 who have chronic insomnia.

#### 6.1.2 Device Administration and Schedule

Patients will be consented and enrolled in person on the enrollment date where they will complete their baseline surveys. Over the following 14 days, patients will complete their baseline sleep diaries. Patients randomized to the PDT will be contacted by the Research Associate (RA) and provided information on how to install the app to their mobile devices and receive a unique access code for the PDT.

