## 5.2 Outcome Variables

### 5.2.1 Primary Outcome Variables

The primary outcomes are a change in the ISI score from baseline to 9-weeks post randomization.

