## 6.3 Study Procedures

### 6.3.1 Study Schedule

Timeline	Event
Enrollment Visit	Informed Consent Hugo and Fitbit account setup Baseline Surveys
Enrollment to 13 days post enrollment	Complete Sleep diaries (at home)
Day 14 post enrollment (+3 days)	Patient randomization Register treatment arm patients onto the PDT
9-weeks post randomization	Follow-up survey
21-weeks post randomization	Follow-up survey
35-weeks post randomization	Follow-up survey
61-weeks post randomization	Follow-up survey Closeout survey

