Upon consent into the study, the patients will receive a Fitbit. For both arms of the study, Hugo will be used as a data collection platform as it aggregates data from multiple real-world data sources, thereby enabling the assessment of patient-reported outcomes, clinical outcomes, and healthcare utilization metrics. All participants will receive materials on sleep hygiene and healthy sleep tips. These sleep hygiene recommendations and healthy sleeping tips include behavioral information regarding getting a good night's sleep (e.g. setting a regular bed-time, getting out of bed if remaining awake, exercising regularly, not smoking). A full list of these tips can be found in **Appendix 1**. Patients will also receive a informational wallet card with study contact information (Appendix 8). Participants randomized to PEAR-003b will receive access to the therapeutic for 9

weeks a in addition to the sleep hygiene material. Post assessment data will be collected post intervention via diaries and questionnaires as outlined in the “Follow-up” section.

Because the Hugo platform obtains patient data through patient portals, all patients who connect will need a YNHH MyChart account. If the patient does not yet have a MyChart account, the RA will assist the patient in creating one. The RA will then assist the patient in linking their YNHH electronic health records to the Hugo platform as well as other health systems where they have received care by showing the study participant how to enter their patient portal credentials, provided that these health systems are connected to the Hugo platform.

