### 6.3.5 On Study Visits

All patients will be asked to use the Hugo platform and Fitbit wearable for the entire 63-week period. Those randomized to PEAR-003b will be asked to complete the 6 core modules in 9 weeks, and at completion will be asked to fill out a questionnaire via Hugo to determine their satisfaction with the process of answering queries and will provide the opportunity for them to offer comments and suggestions for improvement. Patients will be asked to charge their Fitbit for the minimum necessary time during the day and try to wear it for as much time as possible. We will cycle patient reminders about charging the Fitbit for continuous study use based on the anticipated battery life of the Fitbit wearable. Based on our prior experience conducting both SHUTi and Hugo projects, we anticipate being able to stream electronic health record and patient-generated data from the Fitbit into our researcher database using the Hugo platform. The enrollment visit is the only time patients will need to come in for an in-person visit. All subsequent visits will be completed at home. For all patient-reported outcome measures, we will query patients regarding whether they prefer a secure email link or text message link to receive questionnaires at baseline, 9, 21, 35, and 61 weeks. If patients do not respond to this prompt within 24 hours, they will receive an email reminder. Should there be still be no response after an additional 48 hours, the RA will follow up with the patient via phone to ask the patient to complete the unanswered survey.

Patients will be contacted by the RA via phone at 35 and 61 weeks to ascertain any new health systems in which they sought care and the Hugo platform will be checked to ensure that data from those health systems are included (and patients will be asked to link those health systems or provide data, as appropriate). Multiple attempts will be made to contact patients if they are not contacted on the first attempt. Patients will receive automatic reminders to complete questionnaires at 9, 21, 35, and 61 weeks post-randomization via email. Similarly, patients will receive automatic reminders to sync their Fitbit at these time points.

- **Enrollment Visit (in-person) [~3 hours total]:**
  - Informed Consent/study enrollment
  - Fitbit setup
  - Hugo account setup
  - Baseline Surveys: Baseline Questionnaire; ISI; PHQ-8; GAD-7; ESS; PSS-10; SF-12
  - Begin sleep diaries
- **Day 15 post-enrollment**

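### The only pre-treatment ISI is taken at enrolment, nominally 14 to 17 days before randomisation; repeating it just before allocation is a cheap gain in precision

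*Combined protocol and SAP*

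**What the plan says.** Section 5.2.1 defines the endpoint: "The primary outcomes are a change in the ISI score from baseline to 9-weeks post randomization". Section 6.1.2 fixes when baseline is taken: "Patients will be consented and enrolled in person on the enrollment date where they will complete their baseline surveys". The visit list in 6.3.5 shows that the ISI is part of that set: "Baseline Surveys: Baseline Questionnaire; ISI; PHQ-8; GAD-7; ESS; PSS-10; SF-12". The schedule in 6.3.1 agrees, giving for the enrolment visit "Informed Consent Hugo and Fitbit account setup Baseline Surveys".

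The diary period comes next: "Over the following 14 days, patients will complete their baseline sleep diaries" (6.1.2). Randomisation follows, but its day is stated in different ways: "Day 14 post enrollment (+3 days" in 6.3.1, "Day 15 post-enrollment" in 6.3.5, and simply after the 14-day window in 6.3.4. No section schedules an ISI at randomisation.

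Both arms keep diaries and wear a Fitbit in this period. Section 6.3.4 also states, among the enrolment procedures and without a date, "All participants will receive materials on sleep hygiene and healthy sleep tips".

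The primary analysis (6.4.3.1) is a 2 (group) by 2 (time) repeated measures ANOVA, with paired t tests within each arm only if the interaction is significant. Section 6.4.3.2 correlates PDT-arm ISI change with engagement and examines outcomes among patients who complete all six cores.

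**The concern.** The ISI change that the plan analyses begins before the run-in, while treatment begins after it. Two things follow.

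First, a baseline measured closer to allocation would often predict the week-9 score better. If it does, using only the enrolment value gives away precision on the primary contrast in a trial with an effective sample of 80.

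Second, any result that reports change within one arm counts run-in change together with change under treatment. Some run-in change is plausible: patients are recruited around a sleep consult or from a CBT-I waiting list, and then monitor their sleep for two weeks. The documents give no figure for it.

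**Working it through.** **1. Interval.** Week 9 is 9 x 7 = 63 days after randomisation.
- Randomisation on day 14: 14 + 63 = 77 days from baseline ISI, and 14/77 = 18% precedes allocation.
- Day 15: 15/78 = 19%.
- Day 17: 17/80 = 21%.
- Enrolment by Zoom: 6.3.4 lets the Fitbit arrive within 7 days and places the baseline assessment after syncing. If the ISI then falls on day 7 and randomisation on day 14, the share is 7/70 = 10%.

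These are shares of calendar time, not of effect.

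**2. The plan's own figure.** Section 6.4.2 gives d = 0.52 at 90% power with N = 80. By noncentral t, with 40 per arm and two-sided alpha 0.05, a standardised difference of 0.52 has 63% power. That mismatch is a separate matter. I use 0.52 only as a common yardstick, read in raw ISI SD units (an assumption; the plan does not state the unit).

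**3. Precision of the change score.** With unit SDs, the variance of change is 2(1 - r), where r is the correlation of baseline with week 9. The planned two-time-point ANOVA interaction is equivalent to comparing change scores. Assume that the pre-randomisation ISI has r = 0.50, and vary r for the enrolment ISI:

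| r, enrolment ISI | Variance of change | Power, enrolment baseline | Power, re-taken baseline (variance 1.00) |
|---|---|---|---|
| 0.40 | 1.20 | 55% | 63% |
| 0.45 | 1.10 | 59% | 63% |
| 0.50 | 1.00 | 63% | 63% |

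**4. Precision with ANCOVA.** Residual variance is 1 - r1² with the enrolment ISI alone. With both it is 1 - R², where R² = (r1² + r2² - 2·r1·r2·c)/(1 - c²). Here r1 and r2 are the correlations of the enrolment and the pre-randomisation ISI with week 9, and c is their correlation with each other. With r2 = 0.50, 40 per arm and a 0.52-SD difference:

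| r1 | c | Residual variance, one ISI | Both | Power, one ISI | Both | Gain (points) |
|---|---|---|---|---|---|---|
| 0.40 | 0.7 | 0.840 | 0.745 | 70.7% | 75.8% | 5.1 |
| 0.40 | 0.9 | 0.840 | 0.737 | 70.7% | 76.3% | 5.5 |
| 0.45 | 0.8 | 0.798 | 0.743 | 73.0% | 75.9% | 3.0 |
| 0.50 | 0.7 | 0.750 | 0.706 | 75.5% | 78.0% | 2.5 |
| 0.50 | 0.9 | 0.750 | 0.737 | 75.5% | 76.3% | 0.7 |

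The gain from the second ISI is about 1 to 6 points. Replacing the change score by ANCOVA on the enrolment ISI alone gains more: 55% to 71% at r1 = 0.40, and 63% to 76% at 0.50.

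**5. Bias.** I simulated 10,000 trials per scenario at 40 per arm, with an enrolment-randomisation correlation of 0.8, a randomisation-week 9 correlation of 0.5, and a run-in shift of 0 to 0.5 SD common to both arms. For a true effect of 0.52 SD the mean between-arm estimate is 0.52 with either baseline. Type I error is about 5% with either.

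**6. Within-arm change.** In the same simulation, take a control arm with no change after randomisation. For run-in shifts of 0, 0.1, 0.25 and 0.5 SD, the paired test from enrolment declares a time effect in 5%, 8%, 29% and 80% of trials. From the re-taken baseline it does so in about 5%. These rates are not conditioned on a significant interaction, which the plan requires first.

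**The case against.** The strongest reply is that a baseline taken before the run-in is a legitimate choice and does no harm to the primary inference. On bias this stands: change before randomisation has the same expectation in both arms and cancels. A reader might infer from the timing that the primary treatment effect is distorted, and neither the documents nor the simulation supports that. The one qualification concerns last observation carried forward (6.4.5). If dropout differs between arms, a run-in shift does not cancel fully, but on assumed figures (0.25 SD shift x 10-point difference in dropout = 0.025 SD) the remainder is small.

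Two further inferences are tempting and also fail.

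- Because 6.2.1 reads ISI, SOL and WASO together, one might say that ISI change and diary change start from different points. The visit list in 6.3.5 has the ISI first and diaries starting afterwards at enrolment and at every follow-up, so the two measures span about the same interval.
- One might say that the engagement correlations in 6.4.3.2 are distorted. Adding a constant to every patient's change leaves both the Pearson and the Spearman coefficient as they were. Patient-to-patient variation in run-in change could add noise, but nothing in the documents sizes it.

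It is also fair that the paired t tests are conditional and subordinate, and that uncontrolled within-arm change is not a treatment effect from any baseline. The power figures rest on assumed correlations: if both ISI values predict week 9 equally well, the change-score gain is nil. All of this limits the point to a modest one. It does not remove the possible gain in precision or the run-in component in the descriptive change.

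**Conclusion.** The point holds as a cheap improvement. The plan has a single pre-treatment ISI, nominally 14 to 17 days before allocation, and does not repeat it. The primary between-arm test remains valid.

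The supportable consequences are a possible loss of precision and a run-in component in two raw quantities: the conditional within-arm ISI changes and the mean change among six-core completers. A run-in fall of x ISI points overstates each of these by x.

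The second ISI is worth about 1 to 6 points of power in an ANCOVA, or 0 to 8 points in a change-score analysis. This assumes 40 per arm, a 0.52-SD difference, correlations with week 9 of 0.40 to 0.50 for the enrolment ISI and 0.50 for the later one, and 0.7 to 0.9 between the two. None of these correlations, and no figure for run-in drift, comes from the documents.

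**What to change.** - In 6.3.1 and 6.3.5, add an ISI sent through Hugo at the end of the diary window, to be completed before the research associate runs the randomisation.
- In 6.4.3.1, analyse week-9 ISI by ANCOVA with the enrolment and the pre-randomisation ISI as covariates. Where the latter is missing, use the enrolment value. This replaces the 2 x 2 repeated measures ANOVA as the primary model, so it should be stated openly and settled before outcome data are examined.
- Measure descriptive within-arm change, including that among six-core completers, from the pre-randomisation ISI, and say that it is not an estimate of treatment effect.
- Reconcile the randomisation day across 6.1.3, 6.3.1, 6.3.4 and 6.3.5, and state when baseline surveys are completed for patients enrolled by Zoom.

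Cost: one more administration of a questionnaire already delivered through Hugo, and an IRB amendment; no extra visit or staff. Downsides are slight burden, some missing day-14 values (so the fallback mixes two time points in one covariate), and a loss of symmetry: the new baseline ISI would follow diary keeping, whereas the week-9 ISI precedes its diaries. That asymmetry is the same in both arms and does not bias the comparison between them.

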#### 6.1.3 Method of Assignment/Randomization (if applicable)

Patients will be randomized 1:1 to the digital therapeutic or the control arm by the RA using a randomization algorithm via Hugo. Patients will be notified if they are randomized to the treatment arm on day 14 by the RA and will be provided with instruction on how to set up and create their Pear-003b account if randomized to the Pear-003b arm. The study will not employ blinding as patients will need to know if they are completing the treatment

#### 6.1.4 Device Calibration

N/A

#### 6.1.5 Storage Conditions

N/A

#### 6.1.6 Concomitant therapy

Participants are eligible for this study if they are taking traditional sleep medications (e.g. Temazepam, Triazolam, Zaleplon and Zolpidem). Concomitant non-medication treatment programs for insomnia are not allowed during the study. However, non-medication treatments, such as psychotherapy, are allowed for conditions not contraindicated with sleep restriction. (as mentioned in section 5.3.2).

### **6.1.7 Restrictions**

There are no restrictions.

## **6.2 Assessments**

### **6.2.1 Efficacy**

The sleep outcomes identified in this study (Insomnia Severity Index and sleep diary-derived metrics of SOL and WASO) are considered together when evaluating efficacy of the PDT. These measures are part of recent guidelines from the American Academy of Sleep Medicine as outcomes to be considered in evaluation of efficacy and clinical significance.

### **6.2.2 Safety**

N/A. This study has been deemed minimal risk because the probability and magnitude of harm or discomfort anticipated in the research are not greater in and of themselves than those ordinarily encountered in daily life or during the performance of routine physical or psychological examinations or tests and will therefore not be required to be reviewed by a data safety monitoring committee. Information about the minimal risks for this study can be found in Section 3.2.1.

If the study team learns that a participant has clinical depression during screening, or identifies a participant as having clinical depression during the study, the participant will be instructed to schedule an appoint with their primary care clinician; if the participant does not have a primary care clinician, the study team will offer to help the participant schedule an appointment with a primary care clinician at the New Haven Primary Care Consortium (NHPCC).

### **6.2.3 Adverse Events Definition and Reporting**

This protocol presents minimal risks to the subjects and Unanticipated Problems Involving Risks to Subjects or Others (UPIRSOs), including adverse events, are not anticipated. In the unlikely event that such events occur, they will be reported immediately, followed by a written report within 5 calendar days of the PIs becoming aware of the event to the IRB (using the appropriate forms from the website) and any appropriate funding and regulatory agencies. The investigators will apprise fellow investigators and study personnel of all UPIRSOs and adverse events that occur during the conduct of this research project via email as they are reviewed by the PIs. The protocol's research monitor(s), e.g. study sponsors, funding and regulatory agencies, and regulatory and decision-making bodies, will be informed of a data breach within 5 days of the event becoming known to the PI.

### **6.2.4 Pharmacokinetics (if applicable)**

N/A

### 6.2.5 Biomarkers (if applicable)

N/A

## 6.3 Study Procedures

### 6.3.1 Study Schedule

Timeline	Event
Enrollment Visit	Informed Consent Hugo and Fitbit account setup Baseline Surveys
Enrollment to 13 days post enrollment	Complete Sleep diaries (at home)
Day 14 post enrollment (+3 days)	Patient randomization Register treatment arm patients onto the PDT
9-weeks post randomization	Follow-up survey
21-weeks post randomization	Follow-up survey
35-weeks post randomization	Follow-up survey
61-weeks post randomization	Follow-up survey Closeout survey

